### **7.3 Covariates and Subgroups**

Covariates of interest include age. We will evaluate age dichotomized based on the median of the trial participants and continuously in regression models. Race is categorized as White, Black, Hispanic, Asian, American Indian or Alaska Native. Heart rate will be used to dichotomize patients  $\leq 70$  and systolic blood pressure  $\leq 120$  mmHg. Renal function will be dichotomized for subgroups of patients with  $eGFR \geq 60$  ml/min/1.73 m^2.

## 7.4 Missing Data

For data missing from the ADHFD required for the primary or secondary analyses, chart review will be used to identify the missing data. If a patient dies prior to the end of the trial, we will evaluate active medications prior death for the primary and secondary outcomes. No imputation of missing data is planned for the outlined analysis. Any imputation procedures would only be used for exploratory analyses.

[figure not shown]
## 8 Summary of Study Data

All continuous variables will be summarized using the following descriptive statistics: n (non-missing sample size), mean, standard deviation, median, maximum and minimum. The frequency and percentages (based on the non-missing sample size) of observed levels will be reported for all categorical measures. All summary tables will be structured with a column for each treatment in the order (Control, Intervention) and will be annotated with the total population size relevant to that table/treatment, including any missing observations.

### 8.1 Subject Disposition

Participants will be included as active based on presents on ADHFD at baseline and at termination of the study. Participants missing on the final exported ADHFD file will undergo chart review to abstract study variables. Deaths or transfers to other VA healthcare systems will be abstracted for missing patients.

**Figure 1: CONSORT Study Flow Diagram Template**

## 8.2 Derived Variables

We created and utilized an optimization potential score (OPS) to quantify the extent of GDMT optimization. The OPS ranges from 0-10. Scores of 0 indicate a high potential for further optimization. The scoring system is defined as follows and represents the incremental steps a clinician would take to add-on or titrate therapies:

	Points		
	None	Low Dose	Targeted Dose
ACE/ARB/ARNI	0	1	2
Beta-Blocker	0	1	2
MRA	0	1	2
ARNI	0	1	2
SGLT2i	0	-	2

As an example, a patient on target doses of beta-blocker and ARNI but not an MRA or SGLT2i would receive a total of 6 optimization points.

## 8.3 Protocol Deviations

No major deviations from the protocol are anticipated for this study.

## 8.4 Demographic and Baseline Variables

Variables obtained from the ADHFD are available in **Table 2**.

Table 2: Baseline Variables from the Academic Detailing Heart Failure Dashboard	
Name	Legal name
Last 4 Social Security	-
Age	years
Race	White, Black, Hispanic, Asian, American Indian or Alaska Native
Weight	lbs
Primary Care Clinician	Assigned
3M Hospitalization Risk	Percent
3M Hospitalization Rank	Percentile
Heart Failure Hospitalizations	Last 12 months for any VA hospitalization.
Last Heart Failure Discharge	Date
Current Inpatient Status	Yes/No
Recent ED Visit	Last 14 days
Most Recent Left Ventricular Ejection Fraction (LVEF)	Last 3 years based on natural language processing variable construction
Last LVEF Documented Date	Date
Blood Pressure	Most recent recorded in the last year
Blood Pressure Date	Date
Pulse	Most recent recorded in the last year
Pulse Date	Date
Weight	Most recent in last 3 years
Weight Date	Date
Potassium	Most recent in last year
Potassium Date	Date
Magnesium	Most recent in last year
Magnesium Date	Date
Serum Creatinine	Most recent in last year
Serum Creatinine Date	Date
BNP	Most recent in last year
BNP Date	Date
NT-proBNP	Most recent in last year
NT-proBNP Date	Date
Digoxin	Most recent in the last year
Digoxin Date	Date
Estimated glomerular filtration (eGFR)	Race stratified estimates
eGFR Date	Date
ACE/ARB/ARNI	Medication name and dose *last fill must cover preceding 6 weeks **active, suspended, hold or provider hold orders ***Current non-VA medication
Beta-Blocker	"
Aldosterone Antagonist	"
SGLT2i	"
Allergies	To above medications only
Next Primary Care Appointment	Clinic name, date, and time
Next Cardiology Appointment	Clinic name, date, and time
Next Appointment	Next appointment for any clinic within 2 weeks.

Table 3: Expected Baseline Characteristics Presentation Template		
	Control	Intervention
Patient Characteristics		
Age	years	
Female	%	
Race	%	
White	%	
Black	%	
Asian	%	
AI/AN	%	
Mean BP	mmHg	
Systolic >120 mmHg	%	
Mean Pulse	rate	
Pulse >70	%	
Median Weight	lbs	
Mean eGFR		
Medications		
ACE/ARB/ARNI	%	
ARNI	%	
Beta-Blocker	%	
MRA	%	
SGTLT2i	%	
Diuretic	%	
Measurements		
Median Weight (IQR)	lbs	
Mean Pulse (SD)	Beats per minute	
Mean BP (SD)	SBP/DBP mmHg	
Mean Potassium (SD)	mmol/L	
Mean eGFR	ml/minute	
Number of Hospitalizations past 12 months	count	

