### 4.2.2 Secondary outcome

The secondary outcomes of the study will include the following at final evaluation:

1. Active prescriptions for individual classes of GDMT
  - a. ACE/ARB/ARNI
  - b. Beta-Blocker
  - c. MRA
  - d. ARNI
  - e. SGTL2i
2. Hospitalizations
  - a. Total number of any cause hospitalization
  - b. Total number of primary HF hospitalizations
  - c. Proportion of patients with any hospitalization
  - d. Proportion of patients with any HF hospitalization
3. Number of deaths
4. Clinician time spent per patient from opening chart to end of patient-specific intervention and documentation.
5. Health service efficiency
  - a. Number of patients reviewed or contacted per half-day clinic
  - b. Number of medication adjustments (stop, start, titration) per half-day clinic
  - c. Number of laboratory tests ordered per half-day clinic
  - d. Number of imaging/diagnostic procedures ordered per half-day clinic
  - e. Number of referrals for consults/device therapy per half-day clinic
6. Qualitative evaluation of patient surveys who received the intervention.

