### **5.4 Study Assessments**

Data for analysis will be pragmatically ascertained through the variables available in the ADHFD. The ADHFD data will be exported at baseline. To evaluate study outcomes, the ADHFD will be exported again to a secure Excel file 6-months after the last participant receives the intervention. The ADHFD data includes age, race, hospitalization risk scores, number of VA hospitalizations in the past 12 months, vital signs (weight, blood pressure, pulse), laboratory values (potassium, creatinine, BNP, eGFR), active GDMT prescriptions, and upcoming appointments. Sem-structured survey data will be captured by clinicians for only intervention patients. No interim analyses are planned. Longer term secondary evaluations will be evaluated at 1 and 2 year.

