### 10.1 Adverse Events

Specific adverse events of interest include symptomatic hypotension documented in the EHR. Hospitalizations related to heart failure will be captured during the study end using the ADHFD. If patients were removed from the dashboard at 6 months, a chart review will be performed to abstract missing data.

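### The dashboard's one hospitalization count, labelled heart failure but described as any VA admission, can supply at most one of outcomes 2a and 2b

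*SAP*

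**What the plan says.** **Outcomes.** SAP 4.2.2 lists "Total number of any cause hospitalization" (2a) and "Total number of primary HF hospitalizations" (2b) as separate items, with the matching proportions of patients as 2c and 2d. SAP 9.2 adds a hazard ratio for HF hospitalization.

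**Source.** SAP 5.4 says that analysis data come from dashboard variables and that the dashboard is exported a second time to evaluate outcomes. It describes the hospitalization item as "number of VA hospitalizations in the past 12 months". For HF admissions, SAP 10.1 is explicit: "Hospitalizations related to heart failure will be captured during the study end using the ADHFD".

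**Field.** Table 2 in SAP 8.4 contains one hospitalization count. The row is named "Heart Failure Hospitalizations" and described as "Last 12 months for any VA hospitalization". The next row, "Last Heart Failure Discharge", holds a date. The corresponding row in the Table 3 template is "Number of Hospitalizations past 12 months", with no mention of HF.

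**Back-up.** SAP 7.1, 8.1 and 10.1 send patients who are no longer on the dashboard to chart review. SAP 7.4 also provides chart review for data that the dashboard lacks and that a primary or secondary analysis needs.

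**The concern.** Two outcomes that differ only in cause of admission need either two counts or a list of admissions with their causes. The named source offers one count, whose label and description disagree about cause. No section says how an HF admission is told apart from any other.

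Reducing hospitalizations is a stated study objective (SAP 4.1), and an HF hazard ratio is planned. With the field undefined, two analysts working from the same export could assign it to different outcomes, and that choice could be made after the data are seen. A patient who has left the dashboard would be counted by a chart reviewer and a patient still listed by the automated field, with no common rule for cause.

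This point is about the cause of admission and its source. The 12-month look-back of the field is a separate question.

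**Working it through.** The plan states no figure to reproduce here. The check sets the sections side by side and asks what the dashboard fields can yield under each reading of the Table 2 row.

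- **Reading A:** the field counts every VA admission. The description in Table 2, SAP 5.4 and Table 3 favour this.
- **Reading B:** the field counts HF admissions at any VA site. The row label, the neighbouring HF discharge row and SAP 10.1 favour this.

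| Outcome | Reading A | Reading B |
|---|---|---|
| 2a any-cause count | Available, VA admissions only | No dashboard count |
| 2b primary HF count | No dashboard count | Approximately available |
| 2c any admission, yes/no | Available, VA admissions only | Not available from the count |
| 2d any HF admission, yes/no | Possibly, from the last HF discharge date | Available from the count or the date |
| HF hazard ratio, first-event time | Not recoverable after repeat admissions | Not recoverable after repeat admissions |

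Under Reading B, 2b is only approximate because the table does not say that HF must be the primary reason for admission.

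**What the discharge date can do.** If the last HF discharge falls after randomization, the patient had at least one HF discharge in follow-up, which bears on 2d. A single date carries no count, so it cannot give 2b. After two or more HF admissions it shows the latest, so the first-event time is lost.

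**What chart review can do.** For a patient still on the dashboard the count is filled in, so nothing shows as missing and SAP 7.4 is not clearly triggered. SAP 7.1, 8.1 and 10.1 apply chart review to patients who have dropped off. None of these sections gives a rule for classifying cause.

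**Illustration of size (all inputs assumed; none is in the documents).** Let f be the HF share of usual-care admissions, assumed 0.20 to 0.50. Let the true HF rate ratio be 0.70, with no effect on other admissions. If an all-VA count were analysed as the HF count, the rate ratio would be

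f × 0.70 + (1 − f) × 1 = 1 − f × (1 − 0.70).

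- f = 0.20: 1 − 0.20 × 0.30 = 0.94
- f = 0.35: 1 − 0.35 × 0.30 = 0.895
- f = 0.50: 1 − 0.50 × 0.30 = 0.85

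Conversely, if an HF-only count were analysed as any-cause, it would miss 1 − f of admissions, which is 0.80 to 0.50 over the same range. The plan does not say that either substitution will be made. The figures show only what would follow if it were.

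**The case against.** The strongest defence is that the Table 2 row has a coherent meaning. The left column names the variable and the right column gives its window or scope, so the row can mean HF admissions in the past year at any VA site. The next row and SAP 10.1 fit that reading. This stands as far as it goes: the wording is ambiguous, and the label is not shown to be wrong. But that reading leaves 2a and 2c without a dashboard source.

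Second, SAP 7.4 is written by data item and could be read to cover a count that the dashboard lacks. That reading is possible. It does not settle the matter, because the field is populated for listed patients and no cause-of-admission rule is given.

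Third, Table 2 is titled as baseline variables, and SAP 10.1 names only HF admissions, so the any-cause link rests on the general statement in SAP 5.4. That is correct. However, SAP 5.4 plans the second export of the same dashboard for outcomes, and no other list of outcome variables exists.

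Fourth, defining the field and naming a source and cause rule for each outcome might be enough. Defining the field alone would not be, since one count would still lack a source.

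A reader might go further and infer any of three things, none of which the documents support:

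- *Neither outcome measures what its name says.* Under either reading the field roughly matches one of them.
- *2a and 2b collapse into one number.* No section says that both are read from this row.
- *Capture at VA sites differs by arm.* Restriction to VA admissions is documented in SAP 5.4 and Table 2. A difference between arms is conceivable because the intervention can refer patients to cardiology clinics, but nothing shows it, and usual care also includes cardiology appointments.

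**Conclusion.** The concern holds in this form: the named source cannot yield both of the stated counts, and it cannot supply first-event times for the hazard ratio once a patient has repeat HF admissions. Ascertainment would also differ between patients on and off the dashboard. This does not depend on which reading of the row is right, and it goes beyond missing detail.

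The size cannot be established from the documents. The dilution from 0.70 to between 0.94 and 0.85 is an illustration. It depends on an assumed HF share, an assumed effect, no effect on other admissions, and use of an all-VA count for an HF outcome.

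The affected results are secondary. The primary analysis of the optimization potential score does not use this field. The change should be made, but the trial's main conclusion does not depend on it.

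**What to change.** In SAP 5.4 and 10.1:

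1. State what the dashboard hospitalization field counts, and align the Table 2 label, its description and the Table 3 row with that.
2. Take outcomes 2a-2d and the hazard ratio from one dated extract of VA admissions with principal discharge diagnosis, applied identically to all randomized patients in both arms, whether or not they are still on the dashboard.
3. Count 2b, 2d and the hazard ratio by principal HF diagnosis, and 2a and 2c by all admissions.
4. Describe these outcomes as VA hospitalizations unless non-VA admissions are captured the same way in both arms.

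The cost is SAP wording and one data pull for 300 patients. It needs no new visits or staff.

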## 8.5 Treatment Compliance

For secondary analyses, treatment compliance will be estimated using the proportion of days covered (PDC) from VA pharmacy data for the 6 weeks prior to the study termination for each GDMT class of medications.

## 9 Efficacy Analysis

The analysis will evaluate differences between usual care and the intervention arm (intention to treat) in the receipt of active prescriptions for GDMT, hospitalizations, and mortality.

### 9.1 Primary Efficacy Analysis

The primary analysis will evaluate the effectiveness of the proactive panel management intervention compared to usual care using the OPS score 6-months after the last participant in the intervention arm receives the intervention. The difference in the OPS score between usual care and intervention will be estimated using a parametric ANCOVA with baseline OPS as a covariate as well as restricted cubic spline adjusting for baseline age. Age is specified as it may relate to the tolerance and probability of receiving more classes of medications.

## 9.2 Secondary Efficacy Analysis

The secondary efficacy analysis will include the difference in OPS score 6-months after the last intervention using an unadjusted parametric ANCOVA.

Additional secondary analyses include:

- Difference in rates of receipt of each class of GDMT using a two-sample proportions test Pearson's chi-squared test between intervention and usual care assignment.
  - ACE/ARB/ARNI
  - ARNI
  - Beta-blocker
  - MRA
  - SGLT2i
- Hazard ratio for heart failure hospitalization at final evaluation between intervention.

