Outcomes will be assessed at 6-months from the last patient to receive the intervention. The study is powered to detect superiority of the intervention compared to usual care in optimizing GDMT for HFrEF. Treatment assignment is based on 1:1 randomization using fixed blocks (size=6) to assure an equivalent number of patients randomized to the intervention and usual care. Patients are randomized after a list of 300 actionable patients are generated from the ADHFD. Study participant numbers will be assigned to the list of patients sorted by optimization scores in Excel. The supervising statistician (AA) will generate concealed randomization assignments by participant identification numbers. The randomization assignments will be merged with baseline study dataset and exported as password protected Excel and PDF documents. Study investigators will divide the intervention arm into lists of 10 to 15 per half-day clinic. Patients not receiving chart review or phone call attempts will be reassigned to future panel management clinics until all patients receive the intervention. Patients that did not answer phone calls will receive chart review notes for primary care and cardiology clinicians and not be reassigned to future panel management clinics.

Study participants do not require informed consent as determined by the VA IRB review. Patients will receive all accepted standards of care and medications approved by the Food and Drug Administration for HFrEF indications. The VA Subcommittee for Research and Safety found an absence of any declared research-laboratory-based biohazards and granted exemption from continued review. The study will evaluate the effectiveness of the QI intervention, telephone/telemedicine panel management clinics, to more rapidly implement evidence-based care for patients with HFrEF. Patients in the usual care arm will be unaware they are part of the control group for the RCT. Intervention patients nor study staff are blinded to usual care or intervention assignments. Patients that receive the intervention will be informed this is a pilot quality improvement effort with informal consent before proceeding to the clinical interventions. Intervention patients may refuse to participate after being contacted by phone in the intervention.

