Study enrollment is based on the inclusion and exclusion criteria used to filter the ADHFD list. A list of actionable patients with HFrEF will be exported for randomization. The GDMT optimization score will be automated for each patient on the extracted list (**Table 1**). A sample of 300 patients will be selected with the lowest GDMT composite scores. Once the final sample of the study is determined, patients will be randomized to usual care or the intervention. Intervention patients will be divided into smaller lists of 10 to 15 patients. These smaller

lists will be assigned to proactive panel management clinics. Clinicians staffing the intervention clinics will review ADHFD data, review the electronic health record (EHR) and decide whether to proceed to evaluate and recommend treatment over the phone to patients directly. If clinicians did not have sufficient time to review all patients on their clinic list, they will be redistributed to future intervention clinics. Intervention clinics will be held until each patient assigned the intervention has a chart review or attempted telephone contact. A failure to contact a patient will trigger a letter to a patient or electronic communication to their primary care or cardiology clinician.

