## **6 Sample Size**

Assuming a baseline average GDMT optimization score of 2.4 for the included population and a standard deviation of 1.5, we estimate a sample of 300 patients to have 83% power to detect 25% improvement in GDMT optimization scores for the intervention (standard deviation assumed 1.9 for the intervention arm). The primary analysis will be performed using ANCOVA with baseline adjustment for age which should improve the power to detect a difference between treatment arms.

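### The SAP compares receipt of each GDMT class by an unadjusted chi-squared test; stratifying by baseline receipt of that class, which the trial already holds, would gain precision at no data cost, unevenly across classes.

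*SAP*

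**What the plan says.** Active prescription of individual GDMT classes is the first secondary outcome listed in SAP 4.2.2. SAP 9.2 gives its analysis for ACE/ARB/ARNI, ARNI, beta-blocker, MRA and SGLT2i: "Difference in rates of receipt of each class of GDMT using a two-sample proportions test", specified as Pearson's chi-squared, between the assigned arms. No covariate or stratum is named there. SAP 7.3 lists age, race, heart rate, blood pressure and renal function, but not baseline receipt of a class. SAP 8.5 concerns days covered.

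The baseline value is available. SAP 5.4 states "The ADHFD data will be exported at baseline", and the export includes active GDMT prescriptions. Table 2 (SAP 8.4) records medication name and dose by class, with the rule that the "last fill must cover preceding 6 weeks". Table 3 already plans a baseline percentage for each class, with ARNI on its own row.

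The SAP adjusts for baseline where the score is concerned: the primary ANCOVA is fitted "with baseline OPS as a covariate", together with a spline for age (SAP 9.1).

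**The concern.** Whether a patient is on a drug class at the end depends heavily on whether they were on it at the start: users mostly continue, and non-users have to be started. An unadjusted comparison of final proportions counts this predictable between-patient variation as noise. The SAP removes it for the OPS but not for the components of the OPS.

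The class comparisons show which drugs account for any change in the score. If their intervals are wider than the data require, the trial may show that the score moved without being able to say where. The primary conclusion is not at stake.

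The gain cannot be the same for every class. The plan says "A sample of 300 patients will be selected with the lowest GDMT composite scores" and assumes a mean of 2.4 out of 10. That leaves room for common beta-blocker and ACE/ARB use, but not for all five classes to be common.

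**Working it through.** **The plan's only power figure.** SAP 6 gives 83% power for the OPS; nothing is given for class receipt. With a difference of 0.25 × 2.4 = 0.60, SDs of 1.5 and 1.9, 150 per arm and two-sided 5% (alpha is not stated, so assumed), power is 85.9%. The stated 83% is not reproduced exactly but is on the cautious side; about 8% attrition would give 82.9%. This has no bearing on the class comparisons.

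**Inputs.** From the documents: 300 patients, 1:1, permuted blocks of 6 (SAP 5.3), and a list in score order, since "Study participant numbers will be assigned to the list of patients sorted by optimization scores in Excel" (SAP 5.1).

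Assumed, because the documents give no class rates:
- Baseline use: ACE/ARB/ARNI 62%, beta-blocker 68%, MRA 20%, SGLT2i 8%, ARNI 4%. These were set so that the simulated OPS has mean 2.40 and SD 1.46-1.47, against the SAP's 2.4 and 1.5.
- Persistence of baseline users: 85% or 95%.
- New starts among non-users: 15% in usual care, 28% or 35% in the intervention arm.

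**Precision formula.** Let b be baseline use, q persistence, and i0 and i1 the start rates. Final receipt in arm k is pk = bq + (1−b)ik. Per-patient variance terms for the risk difference are:
- unadjusted: p0(1−p0) + p1(1−p1)
- stratified: 2b·q(1−q) + (1−b)[i0(1−i0) + i1(1−i1)]

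*Example: ACE/ARB/ARNI, q = 0.95, starts 15% vs 28%.*
- p0 = 0.62×0.95 + 0.38×0.15 = 0.646; p1 = 0.62×0.95 + 0.38×0.28 = 0.695.
- Unadjusted: 0.2287 + 0.2118 = 0.4405; half-width 1.96√(0.4405/150) = 0.106.
- Stratified: 0.62×0.0950 + 0.38×(0.1275 + 0.2016) = 0.1840; half-width 1.96√(0.1840/150) = 0.069.
- The interval is about 35% narrower. Simulation gives 0.106 to 0.068.

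Simulated half-widths for the other classes in this scenario: beta-blocker 0.102 to 0.065, MRA 0.108 to 0.085, SGLT2i 0.100 to 0.089, ARNI 0.096 to 0.090.

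**Power, chi-squared → CMH.** 10,000 simulated trials per scenario, list sorted by OPS, blocks of 6, no continuity correction:

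| Persistence; starts | ACE/ARB/ARNI | Beta-blocker | MRA | SGLT2i | ARNI |
|---|---|---|---|---|---|
| 85%; 15 vs 28% | .130→.204 | .107→.166 | .469→.614 | .658→.729 | .721→.757 |
| 85%; 15 vs 35% | .249→.395 | .205→.302 | .825→.919 | .946→.970 | .965→.975 |
| 95%; 15 vs 28% | .128→.295 | .101→.230 | .469→.667 | .651→.750 | .708→.763 |
| 95%; 15 vs 35% | .286→.551 | .222→.446 | .822→.939 | .937→.969 | .963→.977 |

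A repeat simulation of the third row agreed to within about 2 points.

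**Error rate.** Under the null with the sorted list, chi-squared rejects .027-.040 of the time for ACE/ARB/ARNI and beta-blocker and .039-.051 for the other three classes. CMH rejects .044-.052 throughout.

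**Other rates.** With a different set of assumed rates and simple randomization, the variance of the risk difference falls 34-49% at 20-70% baseline use, 25-36% at 10%, 10-25% at 5% and 3-12% at 2%. At 5% use with starts of 5% vs 13%, power goes from .508 to .635, so the gain for a rarely used class is not always negligible.

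**The case against.** **The planned test is conventional and valid.** The SAP makes no power or confirmatory claim for class receipt, and the primary analysis already adjusts for baseline OPS and age. This is true: the point is about efficiency in secondary analyses.

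**The largest gains need a larger effect than the SAP designs for.** Score each new start at its minimum points (2 for SGLT2i, 1 for the others). Starts of 15% vs 28% imply an OPS difference of 0.13 × (0.38 + 0.32 + 0.80 + 2×0.92 + 0.96) = 0.56, close to the planned 0.60. Starts of 15% vs 35% imply at least 0.20 × 4.30 = 0.86. Within the 28% scenarios the gains are 7-17 points for ACE/ARB/ARNI and 6-13 for beta-blocker, ending at only 20-30% and 17-23% power. This stands as a caution: the 35% rows are a sensitivity range. MRA still gains 14-20 points in the 28% rows.

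**Sorted blocking already supplies part of the precision.** Under sorted blocks the true sampling SD of the risk difference falls by 14-29% for the two common classes, less than the 21-36% narrowing of the reported interval. The rest is the unadjusted interval being too wide for this design. That is right, and it favors stratifying, because the chi-squared test does not credit the balance the design creates.

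**The rates are assumptions.** One control start rate is applied to every class, although the guidance document (S1, Step 2a) places ARNI after a specified ACE/ARB dose. The size is therefore uncertain at both ends, but the direction is not.

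**Conclusion.** The concern holds. The class comparisons ignore a strong predictor that is already recorded for both arms, and nothing elsewhere in the SAP makes up for it. The cost is wider intervals and lower power on secondary outcomes, with no bias or inflated error.

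The gain is largest in absolute terms for ACE/ARB/ARNI, beta-blocker and MRA, and generally smaller for SGLT2i and ARNI. Stratifying does not rescue the two commonest classes, which remain underpowered in every scenario examined.

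These sizes rest on assumed baseline use, persistence and start rates, tied to the documents only through the OPS mean and SD. Baseline use can be read directly from the baseline export and the gain recomputed. Confidence in the direction is high; confidence in the exact size is moderate at best.

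**What to change.** In SAP 9.2, for each of the five classes:

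- Make the main comparison a CMH test stratified by baseline receipt of that class (yes/no).
- Report the Mantel-Haenszel risk difference, stratified the same way, with its 95% CI. With 1:1 allocation the weights follow stratum size, so it estimates essentially the same marginal difference as the unadjusted comparison.
- Derive baseline ARNI receipt from the medication name in the combined ACE/ARB/ARNI field. Table 3 needs this derivation anyway.
- Keep the Pearson chi-squared test as a sensitivity analysis.

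Leave the unadjusted OPS comparison in SAP 9.2 as it is, since it is the counterpart of the adjusted primary analysis. The change costs SAP wording and a few lines of code per class, with no new data. It should be fixed before outcome data are exported, so that the choice of adjustment cannot be questioned afterwards.

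### SAP 9.2 specifies no covariate for the heart-failure hospitalization hazard ratio, although the baseline export lists a hospitalization-risk score; pre-specified adjustment would bring a modest gain

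*SAP*

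**What the plan says.** The whole specification in SAP 9.2 is one line: "Hazard ratio for heart failure hospitalization at final evaluation between intervention". It gives no model, covariate, time origin, censoring rule or handling of death. SAP 4.2.2 also lists the proportions of patients with any hospitalization and with any heart-failure hospitalization (items 2c and 2d), but SAP 9.2 names no analysis for them.

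Prognostic information is collected at baseline. SAP 5.4 states: "The ADHFD data includes age, race, hospitalization risk scores, number of VA hospitalizations in the past 12 months". Table 2 in SAP 8.4 lists "3M Hospitalization Risk" as a percent, with a percentile rank, and a row labelled "Heart Failure Hospitalizations" that covers the last 12 months. No outcome analysis uses any of these.

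For contrast, SAP 9.1 defines the primary model fully: "parametric ANCOVA with baseline OPS as a covariate as well as restricted cubic spline adjusting for baseline age". SAP 7.3 says "Covariates of interest include age" and adds "We will evaluate age dichotomized based on the median of the trial participants and continuously in regression models", without saying whether the hazard-ratio model is one of those models.

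Allocation is 1:1 in blocks of 6 (SAP 5.3) on a list sorted by optimization score (SAP 5.1). There is no stratification by hospitalization risk.

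**The concern.** Fewer hospitalizations are a stated objective (SAP 4.1), and this hazard ratio is the only hospitalization comparison for which SAP 9.2 gives an analysis. The plan adjusts its primary outcome for the baseline value of that outcome, and SAP 6 expects covariate adjustment to help power. It does not carry the same reasoning over to hospitalization.

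Three things are at stake:

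- **Power.** When patients differ in risk, a Cox model without the risk variable estimates a hazard ratio closer to 1 and rejects somewhat less often.
- **Chance imbalance.** Sorting by optimization score before blocking tends to balance that score but does nothing directly for hospitalization risk. A chance difference in measured risk would stay in the estimate.
- **Pre-specification.** Study staff are not blinded after randomization (SAP 5.3). With the line silent, covariates could be chosen after results are known.

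**Working it through.** **The plan's own figure.** The documents give no power, event count or event rate for this endpoint. The only power figure is 83% for the optimization score (SAP 6). With a difference of 0.25 × 2.4 = 0.6, SD √((1.5² + 1.9²)/2) = 1.712, 150 per arm and two-sided 0.05, I get 85.9%. The stated 83% is slightly conservative and has no bearing here.

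**Inputs.** From the SAP: 300 patients, 150 per arm. Assumed, because not stated: two-sided alpha 0.05; control risk of heart-failure hospitalization 10%, 20% or 30%; true hazard ratio 0.6; hazard ratio per SD of the score 1.5, 2.0 or 2.5.

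**Step 1: what the endpoint can detect.** Schoenfeld: power = Φ(|ln HR| × √E / 2 − 1.96), with |ln 0.6| = 0.511.

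- 30 events: Φ(0.511 × 2.739 − 1.96) = 28.7%
- 45 events: 40.3%
- 60 events: 50.7%
- 80% power needs 121 events.

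**Step 2: chance imbalance.** The between-arm difference in the mean of a standardized score has SD √(2/150) = 0.115. One SD of imbalance shifts the unadjusted log hazard ratio by 0.115 × ln(hazard ratio per SD): 0.047, 0.080 and 0.106 for 1.5, 2.0 and 2.5. The standard error of the log hazard ratio is about 0.44 with 24 events and 0.30 with 49. A 1.96-SD imbalance multiplies the hazard ratio by exp(1.96 × 0.047) = 1.10, exp(1.96 × 0.080) = 1.17 or exp(1.96 × 0.106) = 1.23, or by the reciprocals. On the log scale that is 0.092, 0.157 or 0.207, which is 18%, 31% or 41% of 0.511.

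**Step 3: power with and without the score.** 2,000 simulated trials per row, both Cox models fitted to the same data. The Monte Carlo standard error of a single power is at most √(0.25/2000) = 1.1 points.

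| Control risk (events) | HR per SD of score | Unadjusted | Adjusted | Gain (points) |
|---|---|---|---|---|
| 10% (about 24) | 1.5 | 20.4% | 21.0% | 0.6 |
| | 2.0 | 19.9% | 22.0% | 2.1 |
| | 2.5 | 20.2% | 22.5% | 2.3 |
| 20% (about 49) | 1.5 | 41.6% | 42.1% | 0.5 |
| | 2.0 | 39.8% | 41.3% | 1.5 |
| | 2.5 | 36.7% | 41.4% | 4.7 |
| 30% (about 75) | 1.5 | 56.5% | 58.0% | 1.5 |
| | 2.0 | 52.6% | 58.2% | 5.6 |
| | 2.5 | 47.5% | 59.2% | 11.7 |

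The gain does not come from a smaller standard error (0.436 against 0.437 in the first row). It comes from the estimate: in the last row the median log hazard ratio is −0.445 unadjusted (HR 0.64) and −0.516 adjusted (HR 0.60).

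**Step 4: validity.** With a true hazard ratio of 1 (1,500 trials per setting), both models rejected in 3.8% to 5.9% of trials.

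**Step 5: other assumptions.** At a true hazard ratio of 0.55, with log-risk SD of 0.7 and 1.0, power went from 37% to 40% and from 35% to 41% at 15% control risk, and from 57% to 63% and from 50% to 60% at 25%. Across hazard ratios of 0.55 to 0.70 the gain was about 0–4 points at 24–26 events, 1–7 at 36–39 and 4–11 at 60–66. It fell to about 0–4 points when the score captured risk only imperfectly.

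**The case against.** The best reply is that little is lost. Randomization makes the unadjusted comparison valid, chance imbalance is already part of its standard error, and the gain is smallest when events are few. Even adjusted, power stays at or below about 63% in these settings, so the endpoint does not become decisive. The two hazard ratios also answer different questions: one is marginal, the other conditional on baseline risk, and the marginal one is a legitimate target for a pragmatic trial. All of this stands, and it limits the point to a minor one. It does not remove the case for settling the covariate in advance.

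Several stronger readings are tempting but unsupported:

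- **That the SAP chose an unadjusted analysis.** It is silent. SAP 9.2 says so explicitly when it means an unadjusted analysis of the optimization score, and SAP 7.3 could be read as putting age into this model.
- **That every patient has a score.** The score is a listed dashboard variable of unstated completeness.
- **That the score is the strongest predictor available.** The documents do not say how well it predicts heart-failure admission. Table 2 also lists prior hospitalizations and natriuretic peptides.
- **That chance imbalance is large relative to any plausible effect.** Step 2 shows that even a 1.96-SD imbalance is well below the assumed effect.
- **That adjustment is free.** A missing score could drop randomized patients, and the estimand changes.

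**Conclusion.** The point holds in a limited form. No covariate is specified for this hazard ratio, a baseline risk score is in the export, and randomization is not balanced on it. Under the assumptions above, adjustment gains roughly 0 to 4 points of power with about 25 events, and up to about 4 to 12 points with 60 to 75 events and a clearly prognostic score. With a weak score the gain is only 1.5 points even at about 75 events. Adjustment also removes chance imbalance in measured risk from the estimate. Event rate, true effect and strength of the score are all assumed, since the documents give none of them. Part of the difference between the two hazard ratios is one of estimand and should not be called bias. This is a minor point on a secondary endpoint, and the primary analysis is unaffected.

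**What to change.** In SAP 9.2, before outcome data are examined:

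1. Specify a Cox model for first heart-failure hospitalization, with randomization as time origin, and with arm and the baseline 3M risk score as one continuous covariate on the log or logit scale.
2. Use the same covariate in the analysis of the proportions hospitalized (SAP 4.2.2, items 2c and 2d).
3. State how death before a first hospitalization is handled.
4. State a rule for a missing baseline score that keeps every randomized patient in the model and is applied without regard to arm. SAP 7.4 allows imputation only in exploratory analyses, so it needs a matching exception if the rule fills in values.
5. Report the unadjusted hazard ratio alongside.
6. Say whether the age statement in SAP 7.3 applies to this model.

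The cost is SAP wording and no new baseline data. The downsides are that the adjusted hazard ratio is conditional on baseline risk, and that the gain will be small if events are few or the score predicts weakly.
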